#### 5.6.2.6 Finkelstein-Schoenfeld Analysis of All-Cause Death and Recurrent HF Hospitalization

The hierarchy of all-cause death and recurrent HF hospitalization will be analyzed using the Finkelstein-Schoenfeld method. Hospitalizations that are adjudicated by the CEC as related to HF using the pre-specified protocol definition will be included in the analysis.

The null and alternative hypotheses are stated as:

 $\mathbf{H_0}$ :  $\lambda_{D,Death} = \lambda_{C,Death} \mathbf{AND} \lambda_{D,Hosp} = \lambda_{C,Hosp}$ 

 $H_1$ :  $\lambda_{D,Death} \neq \lambda_{C,Death}$  **OR**  $\lambda_{D,Hosp} \neq \lambda_{C,Hosp}$ 

Where  $\lambda_{D,Death}$  and  $\lambda_{C,Death}$  represent the rate of all-cause mortality in the Device and Control groups respectively.  $\Lambda_{D,Hosp}$  and  $\lambda_{C,Hosp}$  represent the rate of recurrent HF hospitalizations in the Device and Control groups respectively.

This endpoint will be analyzed when the last subject completes 12 months of follow-up. All available follow-up through 24 months at the time of data cut-off will be included in the analysis. These composite hypotheses will be analyzed using the method of Finklestein and Schoenfeld with death higher in the hierarchy than recurrent HF hospitalizations.

Specifically, for each pair of subjects (say subjects i and j), define a score  $u_{ij}$  in the following manner:

- If subject i is known to have experienced death at a later date than subject j, then  $u_{ij} = 1$  (if subject j is known to have experienced death at a later date, then  $u_{ij} = -1$ ). This determination would happen if death dates are available for both subjects, or if one subject was censored at a later time than the death time for the other.
- If it is not known which subject has gone longer without death, then compare the number of recurrent HF hospitalizations for the two subjects within the shorter of the two follow-up durations. If subject i has fewer hospitalizations than subject j, then  $u_{ij} = 1$ ; (if subject j is known to have fewer hospitalizations, then  $u_{ij} = -1$ ). If subject i has same number of hospitalizations as subject j, then compare the time to the first hospitalization. If subject i is known to have the first hospitalization at a later date than subject j's first hospitalization, then  $u_{ij} = 1$  (if subject j is known to have the first hospitalization at a later date than subject i's first hospitalization, then  $u_{ij} = -1$ )
- For ties,  $u_{ij} = u_{ji} = 0$ . And in all cases,  $u_{ij} = -u_{ji}$ .

Note that the score looks first for a difference in freedom from death. If there is no difference in this measure, then the score looks for difference in the rate and timing of recurrent hospitalizations for HF. The final test statistic is based on the sum of the scores for subjects in the Device group. If we let  $D_i = 1$  for subjects in Device group and let  $D_i = 0$  for subjects in the Control group, we define the statistic using the score described above:

$$T = \sum_{i=1}^{n} U_i D_i$$

where

$$\mathbf{U}_{\mathbf{i}} = \sum_{i \neq j} u_{ij}$$

The mean of the test statistic is zero under the null hypothesis of no difference between Device and Control. Finkelstein and Schoenfeld derive the variance for this statistic:

$$V = \frac{n_D(n - n_D)}{n(n - 1)} \sum_{i=1}^{n} U_i^2$$

where, nD is the number of subjects in the Device group. The null hypothesis will be

rejected at the two-sided significance level of 5% favoring the Device group if  $\overline{V}^{1/2}$  is greater than the upper 97.5th percentile of the standard normal distribution.

Furthermore, the unmatched win-ratio approach will be used to evaluate the composite endpoint of death and recurrent HF hospitalizations through 24 months at the time of data cut-off.

Specifically, each pair of subjects (say subjects i and j) can be classified into one of categories (a), (b), (c), (d), or (e):

- (a) Death in the Device group first.
- (b) Death in the Control group first.
- (c) More HF hospitalizations in the Device group (in the case of tie, the first HF hospitalization in the Device group occurs first).
- (d) More HF hospitalization in the Control group (in the case of tie, the first HF hospitalization in the Control group occurs first).
- (e) None of the above.

The composite endpoint results are summarized by  $N_a$ ,  $N_b$ ,  $N_c$ ,  $N_d$ ,  $N_e$ , the number of pairs in categories (a), (b), (c), (d), and (e), respectively. Based on death and HF hospitalization, respectively,  $N_W = N_b + N_d$  is the number of "winners" for the Device group while  $N_L = N_a + N_c$  is the number of "losers" for the Device group. The "win ratio" is defined as the number of "winners" divided by the number of "losers", i.e.,  $R_W = N_W/N_L$ .

The estimation of the win ratio and 95% confidence interval will be provided to estimate the treatment effect of the composite endpoint of all-cause death and HF hospitalizations through 24 months.

#### **5.6.2.7** Recurrent Hospitalization - all-cause

Treatment with the MitraClip device may reduce the risk of recurrent all-cause hospitalization.

## **Hypothesis:**

The null and alternative hypotheses are stated as:

 $H_0$ : RRR = 0 vs.

 $\mathbf{H_1}$ : RRR  $\neq 0$ 

where RRR is the relative risk reduction in the rate of recurrent hospitalization due to treatment with the MitraClip device. All hospitalizations will be included as events in the analysis.

The Joint Frailty Model method will be used to model the recurrent hospitalization data and estimate the RRR.

RRR = (1- Hazard Ratio of Device vs. Control) =  $(1 - e^{\beta})$  where  $\beta$  is the regression coefficient of the recurrent hospitalization in the JFM model.

This endpoint will be analyzed when the last subject completes 12 months of follow-up. All available follow-up through 24 months at the time of data cut-off will be included in the analysis. Subjects who do not experience any hospitalizations will be censored on their data cut-off date. Subjects who die will be censored on the date of death. Subjects who withdraw from the trial without a hospitalization will be censored on the date of withdrawal.

The null hypothesis is rejected if the regression coefficient for the Device group is significant at the two-sided significance level of 5%. The two-sided 95% confidence interval is calculated as RRR  $\pm$   $Z_{\alpha/2} \times$  SE where RRR and SE are estimated from the Joint Frailty Model and  $Z_{\alpha/2} = 100(1-\alpha/2)$ th percentile of the standard normal distribution. Beneficial treatment effect is established if the lower two-sided 95% confidence bound of the relative risk reduction is greater than zero.

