6.7 Randomization

Before randomization:

- Echocardiography Core Lab must confirm MR severity
- Eligibility Committee must confirm that the subject is on optimal therapy including GDMT and is not appropriate for mitral valve surgery according to local site standards either at baseline or if the subject deteriorates and/or MR increases in severity during follow-up
- Site must reconfirm that subject meets eligibility criteria after Eligibility Committee approval and all baseline tests and assessments must be completed (within 14 prior to randomization)

If screening TEE shows intracardiac mass, thrombus or vegetation, or the Eligibility Committee determines subject requires additional treatment before consideration for the trial, the subject may be deferred and reconsidered for the trial, at which time the TEE must be repeated.

Subjects will be randomized or assigned as a roll-in through the eCRF database. The following baseline information must be captured for registered subjects on the appropriate eCRFs:

- Subject medical history and risk factors
- Current cardiovascular medications
- Physical measurements and vital signs (e.g. weight, height, heart rate, blood pressure and temperature)

6.8 “Treatment” Visit (Device Group or Roll-in Subjects)

For Device group or roll-in subjects, the MitraClip procedure will be performed during the “Treatment” visit. For randomized subjects, the MitraClip procedure must be completed between 1 and 14 days after randomization.

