8.1.2 Serious Adverse Event

If the AE meets any of the criteria below, it is regarded as serious adverse event (SAE).

- a) Led to a death,
- b) Led to a serious deterioration in health that either:
 - 1) Resulted in a life-threatening illness or injury, or
 - 2) Resulted in a permanent impairment of a body structure or a body function, or
 - 3) Required in-patient hospitalization or prolongation of existing hospitalization, or
 - 4) Resulted in medical or surgical intervention to prevent life threatening illness or injury or permanent impairment to a body structure or a body function.
- c) Led to fetal distress, fetal death or a congenital abnormality or birth defect.
- d) An important medical event that may not result in death, be life-threatening, or require hospitalization but may be considered serious when, based upon appropriate medical judgment, may jeopardize the subject and/or may require intervention to prevent one of the outcomes listed in this definition

Note 1: This includes device deficiencies that might have led to a serious adverse event if a) suitable action had not been taken or b) intervention had not been made or c) if circumstances had been less fortunate. These are handled under the SAE reporting system.

Note 2: A planned hospitalization for pre-existing condition, or a procedure required by the Clinical Investigation Plan, without a serious deterioration in health, is not considered to be a serious adverse event.

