The Angiotensin Receptor-Nepriylsin Inhibitor (ARNI) Sacubitril/Valsartan (Entresto™) and the sinoatrial node modulator Ivabradine (Corlanor™) may be used as specified in the 2016 update* to the 2013 ACCF/AHA Guideline for the Management of Heart Failure. Use of these two agents is not required. However, if used, these drugs must be applied in accordance with the CIP as any other major change of GDMT described in the CIP. Specifically, after a major change in medication or dose (and stabilization on the maximum dose tolerated), a TTE is required after 30 days to ensure that the subject still has symptomatic functional MR ($\geq 3+$), and meets all criteria for enrollment. Per the 2016 Guideline update, ACE-I remains a Class I indication, and a subject should not be on both ACE-I and ARNI.

HOSPITALIZATION (ALL-CAUSE)

Defined as admission to inpatient unit or ward in the hospital for at least 24 hours, including emergency department stay. Excludes hospitalizations planned for pre-existing conditions, unless there is worsening in the baseline condition.

Hospitalizations will be adjudicated by the Clinical Events Committee as Heart Failure or Other Cardiovascular hospitalization (see definitions below for Heart Failure and Other Cardiovascular hospitalizations).

HEART FAILURE HOSPITALIZATION

Defined as an event that meets the following criteria of either (A and B and C) or D:

A) Requires hospitalization with treatment in any inpatient unit or ward in the hospital for at least 24 hours, including emergency department stay,

AND

B) Subject has clinical signs and/or symptoms of heart failure, including new or worsening dyspnea, orthopnea, paroxysmal nocturnal dyspnea, increasing fatigue, worsening functional capacity or activity intolerance, or signs and/or symptoms of volume overload,

AND

C) Results in intravenous (e.g., diuretic or vasoactive therapy) or invasive (e.g., ultrafiltration, IABP, mechanical assistance) treatment for heart failure.

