For the purpose of the Clinical Investigational Plan, overnight stays at nursing home facilities, physical rehab or extended care facilities, including hospice, do not meet the Clinical Investigational Plan definition of hospitalization. All hospitalizations, including the index hospitalization for the MitraClip procedure, if complicated by acute worsening heart failure that would have prompted an admission to hospital for heart failure, AND requires intravenous or invasive treatment AND hospitalization is extended by 24 hours, as defined above, will also be considered a heart failure hospitalization. Elective heart failure “tune-ups” that occur following the MitraClip procedure and prolong hospitalization will not count as a heart failure hospitalization.

OR

D) Subject arrives in emergency department with clinical presentation meeting the criteria of heart failure, but dies in the emergency department before hospital admission.

OTHER CARDIOVASCULAR HOSPITALIZATION

Defined as treatment in any inpatient unit or ward in the hospital for at least 24 hours, including emergency department stay for conditions such as coronary artery disease, acute myocardial infarction, hypertension, cardiac arrhythmias, cardiomegaly, pericardial effusion, atherosclerosis and peripheral vascular disease, not related to heart failure as defined.

NON-CARDIOVASCULAR HOSPITALIZATION

Hospitalizations that are not heart failure or other cardiovascular hospitalizations, as defined above, will be categorized as non-cardiovascular hospitalizations.

INDEX PROCEDURE

The procedure in which the MitraClip device implant is first attempted. First attempt of the MitraClip is when the subject is prepared for the procedure and groin is punctured for the transseptal procedure.

LOCAL SITE HEART TEAM

The Local Site Heart Team must consist of, at a minimum, the CT Surgeon and Heart Failure specialist investigators.

MAJOR BLEEDING

Major bleeding is defined as bleeding \geq Type 3 based on a modified Bleeding Academic Research Consortium (BARC)²⁰ definition:

- Type 3
 - Type 3a
 - Overt bleeding plus hemoglobin drop of 3 to <5 g/dL* (provided hemoglobin drop is related to bleed)
 - Any transfusion with overt bleeding
 - Type 3b
 - Overt bleeding plus hemoglobin drop ≥ 5 g/dL* (provided hemoglobin drop is related to bleed)
 - Cardiac tamponade
 - Bleeding requiring surgical intervention for control (excluding dental/nasal/skin/hemorrhoid)
 - Bleeding requiring intravenous vasoactive agents

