#### 5.6.1.1 Intention to Treat Analysis (Primary Analysis)

This analysis will be performed in the ITT population. Subjects who do not experience any HF hospitalizations and are alive will be censored on their data cut-off date. Subjects who die will be censored on the date of death. Subjects who withdraw from the study without experiencing a HF hospitalization will be censored on the date of withdrawal. Duration of follow-up will be calculated from the date of randomization. For a sensitivity analysis, duration of follow-up will also be calculated from the date of the "Treatment" visit or the randomization date if the "Treatment" visit is missing.

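### All-cause hospitalization endpoint: no rule for the Device index admission, so an index stay prolonged by a serious non-HF complication adds no event

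*SAP*

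**What the plan says.** **Event rule.** SAP 5.6.2.7 and protocol 7.4.7 carry the same sentence: "All hospitalizations will be included as events in the analysis". Neither mentions the index admission.

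**Definition.** Protocol Appendix A, under all-cause hospitalization: "Defined as admission to inpatient unit or ward in the hospital for at least 24 hours, including emergency department stay". It continues: "Excludes hospitalizations planned for pre-existing conditions, unless there is worsening in the baseline condition".

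**Index-stay rule.** The only one is inside Appendix A's definition of heart failure hospitalization. It covers stays "including the index hospitalization for the MitraClip procedure, if complicated by acute worsening heart failure", and requires that the worsening would have led to an admission, that intravenous or invasive treatment was needed, and that the stay was extended by 24 hours.

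**Related wording.** The note to the serious adverse event definition (protocol 8.1.2) names two kinds of planned stay: "A planned hospitalization for pre-existing condition, or a procedure required by the Clinical Investigation Plan". Appendix A's all-cause definition names only the first.

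**Timing.** Protocol 6.8 states that "the MitraClip procedure must be completed between 1 and 14 days after randomization". For the primary effectiveness analysis, SAP 5.6.1.1 states: "Duration of follow-up will be calculated from the date of randomization". SAP 5.6.2.7 gives no time origin of its own.

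**Role.** SAP 5.9 tests this endpoint sixth of ten in a fixed order, for labeling claims.

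**The concern.** Only the Device arm has a planned admission built into early follow-up, and the all-cause endpoint has no rule for it. Once the index stay is excluded as planned, a non-HF complication during it cannot become an event: the Appendix A exception is limited to worsening of the baseline condition, and a longer stay is not a new admission. The same complication in a Control subject at home leads to an admission and is counted. An index stay complicated by worsening heart failure does count as a heart failure hospitalization, so the gap is specific to non-HF procedural morbidity, such as stroke, tamponade, major bleeding or vascular injury.

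The result of a confirmatory test may turn on the rule chosen. If this endpoint fails, NYHA class, LVEDV, mortality superiority and the 30-day composite cannot be claimed. Leaving the rule open also allows it to be settled after results by arm are known.

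**Working it through.** **1. Inputs.** SAP 5.8.4.8: 1.9 (Control) and 1.4 (Device) all-cause hospitalizations per subject per 12 months, 610 subjects, about 80% power, 12-month mortality 27% and 22%. SAP 5.6.2.7: two-sided 5% test. SAP 5.8.2: 7.5% attrition at 12 months, follow-up 12 to 24 months, shared gamma frailty with mean 1, variance 1 and exponent 1.

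**2. Reproducing the plan's figure.** RRR = 1 - 1.4/1.9 = 26.3%. A joint frailty simulation with these inputs (305 per arm, 600 runs per pattern, Monte Carlo standard error about 1.6 points) gives power of 82.0% with everyone followed 24 months, 78.5% with a mix, and 80.3% with follow-up uniform on 12 to 24 months. Three patterns were used because the SAP does not give the early accrual numbers. The stated 80% therefore corresponds to no added index event in the Device arm.

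**3. Share of index stays that would count.** The documents give none. SAP Table 2 assumes stroke 2%, MI 2% and device-related non-elective surgery 3% by 30 days, together 7%. Some of these would fall after discharge, and Table 1 assumes under 0.1% for such surgery at 12 months, so 7% is only a guide to scale. I assume x = 0.05 to 0.15 extra events per Device subject.

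**4. Effect on the RRR.** With T years at risk per subject (T = 1 and 1.5 assumed), RRR = 1 - (1.4T + x)/(1.9T).

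**5. Effect on power by scaling.** At 80% power the non-centrality is 1.96 + 0.84 = 2.80 for log(1.9/1.4) = 0.305. Scale it by the new log ratio and take Φ(scaled value - 1.96).

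| T | x | Rate ratio | RRR | Log ratio | Non-centrality | Power |
|---|---|---|---|---|---|---|
| 1 | 0.05 | 1.45/1.90 | 24% | 0.270 | 2.48 | 70% |
| 1 | 0.15 | 1.55/1.90 | 18% | 0.204 | 1.87 | 46% |
| 1.5 | 0.05 | 2.15/2.85 | 25% | 0.282 | 2.58 | 73% |
| 1.5 | 0.15 | 2.25/2.85 | 21% | 0.236 | 2.17 | 58% |

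**6. Check by simulation.** Adding one event on days 1 to 14 for 10% of Device subjects (mixed follow-up, 300 runs) gives a hazard ratio of 0.79 and 61% power with a constant baseline, and 0.80 and 59% with a baseline that changes at day 14. Without the added events the hazard ratio is 0.74. This agrees with scaling at x = 0.10 and T = 1: 1.50/1.90 = 0.79, power 58%.

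These figures show how far the test depends on the counting rule. They do not show that the sample size is too small.

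**The case against.** **The literal reading.** A reader might infer that every Device index admission counts. One extra event each would give an RRR of 1 - 2.4/1.9 = -26% over one year and 1 - 3.8/3.8 = 0% over two; in the simulation the hazard ratio is about 1.3 and power is zero. The documents do not support this as the intended analysis. All-cause hospitalization is a defined term in Appendix A, the SAP sentence most naturally means all causes as opposed to heart failure only, and the planning power reproduces with no added index event. Stays under 24 hours would not qualify, and no length of stay is given. The literal reading only shows why the sentence needs correcting.

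**The definition is arm-neutral.** It counts admissions, and a complication during a Control subject's planned stay is treated the same way. That is true of the wording, but only the Device arm has a planned stay by design.

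**Procedural harm is reported elsewhere.** It appears in the 30-day composite, procedure-related adverse events, major bleeding, days alive and out of hospital, and the stroke, vascular and renal comparisons in SAP Appendix A. The harm is therefore not hidden. However, the composite is a single-arm test against 80% and comes last in the sequence, and the others are descriptive. None corrects the between-arm test of all-cause hospitalization.

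**Counting any prolongation would overcorrect.** A day added for nausea or fever would count against the Device, although it would not admit a Control subject. This stands, and the fix keeps a severity test for that reason.

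**Limits of the documents.** The Clinical Events Committee manual is a separate document, so a rule may exist there. The 5-15% has no source.

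**Conclusion.** The concern holds in a limited form. Neither document says how the index admission enters this endpoint. Under the natural reading it is excluded, although even that is not explicit, because Appendix A does not name protocol-required procedures as the note in protocol 8.1.2 does. The stated definition then omits serious non-HF complications that prolong the index stay, and the omission favours the Device arm.

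If 5-15% of Device subjects had such a stay, the planned 26% RRR would be about 18-25% and power about 46-73%. These sizes rest on the assumed share, on 1 to 1.5 years at risk, and on time running from randomization as in the primary analysis. They are conditional illustrations, not forecasts. The primary effectiveness endpoint is not affected. This should be corrected before results by arm are seen.

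**What to change.** In SAP 5.6.2.7, replace the sentence on which hospitalizations are events with:

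> Hospitalizations from randomization that meet the Appendix A all-cause definition are events. The planned index MitraClip admission is not itself an event, but counts as one event, dated at onset, if it is complicated by an adverse event that would by itself have prompted a hospital admission and that extends the stay by at least 24 hours, as adjudicated by the CEC. The same rule applies to any planned stay in either arm.

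This extends the principle of Appendix A's heart failure rule to other complications, keeps trivial one-day extensions out, and states the time origin. Align the matching sentence in protocol 7.4.7.

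If the sponsor keeps Appendix A unchanged for the main test, pre-specify this count as an ITT sensitivity analysis reported beside it.

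The cost is some extra committee review and a slightly less favourable RRR. Prolonged hospitalization is already a serious adverse event criterion, and the committee already adjudicates hospitalizations, so the added work should be small.

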#### 5.7 Analysis of Additional Descriptive Endpoints

All additional endpoints in this section will be reported with descriptive statistics. Continuous endpoints will be summarized using the following: mean, standard deviation, median, the first and third quartiles, range, and the 95% confidence interval for the population mean using the normal approximation. Categorical endpoints will be summarized as proportions in the form of fractions and percent. The 95% confidence interval for a population proportion will be constructed using the Clopper-Pearson exact method. The 95% confidence interval for the difference of two proportions will be constructed using the Newcombe score method. Other analyses are specified under each category of additional descriptive endpoints.

